8.7. Biopsies

The objective of this portion of the study is to correlate histologic/immunohistologic analyses of biopsy samples to patient responses and observed toxicities. Voluntary participation in this portion of the protocol is mandatory for all study participants. All patients will have a tumor assessment on the initial tumor sample via a standard mutation biomarker panel (MD Anderson 46 gene panel, foundation one panel). Assessment can be conducted from any prior biopsy or from the mandatory tumor biopsy sample, if available. When it is feasible (sufficient biopsy material and blood sample), we will examine, tumor mutational burden by whole exome sequencing and TIL profiling by flow cytometry. We will evaluate whether tumor mutational burden and/or TILs correlates with improved clinical outcomes and response criteria. Additionally, we will determine if radiation enhances the tumor DNA availability in blood compared to baseline.

This study will be done in collaboration with Interventional Radiology Investigators. Biopsies can be obtained 1-2 weeks prior to therapy initialization, at week 1 of cycle 2 (\pm 1 week) for groups 1 and 3 or at week 3 of cycle 2 for group 2 OR at any time at the discretion of the treating physician and the PI for research and / or due to medical necessity. See study calendars for tentative schedules (Section 12 Study Calendars).

9. Adverse Event Reporting

An Adverse Event (AE) is the appearance or worsening of any undesirable sign, symptom, or medical condition occurring after starting the study drug even if the event is considered not to be related to the study drug. Medical conditions/diseases present before starting the study drug are only considered adverse events if they worse after starting the study drug. Abnormal laboratory values or test results constitute adverse events only if they include clinical signs or symptoms, are considered clinically significant, or require therapy.

The investigator (or physician designee) is responsible for verifying and providing source documentation for all adverse events and assigning the attribution for all adverse events for subjects enrolled.

The causal relationship to study drug is determined by a physician and should be used to assess all adverse events (AE). The causal relationship can be one of the following:

Related: There is a reasonable causal relationship between study drug administration and the AE.

Not related: There is not a reasonable causal relationship between study drug administration and the AE.

The term "reasonable causal relationship" means there is evidence to suggest a causal relationship.

Adverse events can be spontaneously reported or elicited during open-ended questioning, examination, or evaluation of a subject. (In order to prevent reporting bias, subjects should not be questioned regarding the specific occurrence of one or more AEs.)

Non-serious Adverse Event

- Non-serious Adverse Events (AE) are to be provided to BMS in aggregate via interim or final study reports as specified in the agreement or, if a regulatory requirement [eg, IND US trial] as part of an annual reporting requirement.
- Non-serious AE information should also be collected from the start of a placebo lead-in period or other observational period intended to establish a baseline status for the subjects.

A ***non-serious adverse event*** is an AE not classified as serious.

Non-serious Adverse Event Collection and Reporting

The collection of non-serious AE information should begin at initiation of study drug. All non-serious adverse events (not only those deemed to be treatment-related) should be collected continuously during the treatment period and for a minimum of **100** days following the last dose of study treatment.

Non-serious AEs should be followed to resolution or stabilization, or reported as SAEs if they become serious. Follow-up is also required for non-serious AEs that cause interruption or discontinuation of study drug and for those present at the end of study treatment as appropriate.

Laboratory Test Abnormalities

All laboratory test results captured as part of the study should be recorded following institutional procedures. Test results that constitute SAEs should be documented and reported to BMS as such.

The following laboratory abnormalities should be documented and reported appropriately:

- any laboratory test result that is clinically significant or meets the definition of an SAE
- any laboratory abnormality that required the participant to have study drug discontinued or interrupted
- any laboratory abnormality that required the subject to receive specific corrective therapy.

It is expected that wherever possible, the clinical rather than laboratory term would be used by the reporting investigator (eg, anemia versus low hemoglobin value).

Potential Drug Induced Liver Injury (DILI)

Standard medical practice in identifying and monitoring hepatic issues should be followed.

Potential drug induced liver injury is defined as:

- 1) ALT (ALT or AST) elevation > 3 times upper limit of normal (ULN)

AND

- 2) Total bilirubin > 2 times ULN, without initial findings of cholestasis (elevated serum alkaline phosphatase)

AND

- 3) No other immediately apparent possible causes of ALT elevation and hyperbilirubinemia, including, but not limited to, viral hepatitis, pre-existing chronic or acute liver disease, or the administration of other drug(s) known to be hepatotoxic.

Wherever possible, timely confirmation of initial liver-related laboratory abnormalities should occur prior to the reporting of a potential DILI event. All occurrences of potential DILIs, meeting the defined criteria, must be reported as SAEs.

Woman of Childbearing Potential (WOCBP)

A woman is considered fertile following menarche and until becoming post-menopausal unless permanently sterile. Permanent sterilization methods include hysterectomy, bilateral salpingectomy, and bilateral oophorectomy.

Women in the following categories are not considered WOCBP

- Premenarchal
- Premenopausal female with 1 of the following:
 - Documented hysterectomy
 - Documented bilateral salpingectomy
 - Documented bilateral oophorectomy

Note: Documentation can come from the site personnel's review of the participant's medical records, medical examination, or medical history interview.

- Postmenopausal female
 - A postmenopausal state is defined as 12 months of amenorrhea in a woman over age 45 years in the absence of other biological or physiological causes. In addition, females under the age of 55 years must have a serum follicle stimulating hormone, (FSH) level > 40 mIU/mL to confirm menopause.

Note: Females treated with hormone replacement therapy, (HRT) are likely to have artificially suppressed FSH levels and may require a washout period in order to obtain a physiologic FSH level. The duration of the washout period is a function of the type of HRT used. The duration of the washout period below are suggested guidelines and the investigators should use their judgement in checking serum FSH levels.

- 1 week minimum for vaginal hormonal products (rings, creams, gels)
- 4 week minimum for transdermal products
- 8 week minimum for oral products

Other parenteral products may require washout periods as long as 6 months. If the serum FSH level is > 40 mIU/ml at any time during the washout period, the woman can be considered postmenopausal.

Contraception Guidance for Female Participants of Child Bearing Potential

One of the highly effective methods of contraception listed below is required during study duration and until the end of relevant systemic exposure. For BMS-986156 monotherapy or in combination therapy treatment with nivolumab is defined as BMS-986156 plus 5 half-lives plus 30 days (duration of ovulatory cycle), for a total of **160 days** post treatment completion. Local laws and regulations may require use of alternative and/or additional contraception methods.

Highly Effective Contraceptive Methods That Are User Dependent

Failure rate of <1% per year when used consistently and correctly.^a

- Combined (estrogen- and progestogen-containing) hormonal contraception associated with inhibition of ovulation^b
 - oral
 - intravaginal
 - transdermal
- Progestogen-only hormonal contraception associated with inhibition of ovulation^b
 - oral
 - injectable

Highly Effective Methods That Are User Independent

- Implantable progestogen-only hormonal contraception associated with inhibition of ovulation^b
- Intrauterine device (IUD)^c
- Intrauterine hormone-releasing system (IUS)^c
- Bilateral tubal occlusion
- Vasectomized partner

A vasectomized partner is a highly effective contraception method provided that the partner is the sole male sexual partner of the WOCBP and the absence of sperm has been confirmed. If not, an additional highly effective method of contraception should be used.

- Sexual abstinence

Sexual abstinence is considered a highly effective method only if defined as refraining from heterosexual intercourse during the entire period of risk associated with the study treatment. The reliability of sexual abstinence needs to be evaluated in relation to the duration of the study and the preferred and usual lifestyle of the participant.

- It is not necessary to use any other method of contraception when complete abstinence is elected.
- WOCBP participants who choose complete abstinence must have a pregnancy test.
- Acceptable alternate methods of highly effective contraception must be discussed in the event that the WOCBP participants chooses to forego complete abstinence

NOTES:

- ^a Typical use failure rates may differ from those when used consistently and correctly. Use should be consistent with local regulations regarding the use of contraceptive methods for participants participating in clinical studies.
- ^b Hormonal contraception may be susceptible to interaction with the study treatment, which may reduce the efficacy of the contraceptive method. Hormonal contraception is permissible only when there is sufficient evidence that the IMP and other study medications will not alter hormonal exposures such that contraception would be ineffective or result in increased exposures that could be potentially hazardous. In this case, alternative methods of contraception should be utilized.
- ^c Intrauterine devices and intrauterine hormone releasing systems are acceptable methods of contraception in the absence of definitive drug interaction studies when hormone exposures from intrauterine devices do not alter contraception effectiveness

Less Than Highly Effective Contraceptive Methods That Are User Dependent

Failure rate of >1% per year when used consistently and correctly.

- Male or female condom with or without spermicide. Male and female condoms cannot be used simultaneously
- Diaphragm with spermicide
- Cervical cap with spermicide
- Vaginal Sponge with spermicide
- Progestogen-only oral hormonal contraception, where inhibition of ovulation is not the primary mechanism of action

Unacceptable Methods of Contraception

- Periodic abstinence (calendar, symptothermal, post-ovulation methods)
- Withdrawal (coitus interruptus).
- Spermicide only
- Lactation amenorrhea method (LAM)

Contraception Guidance for Male Participants with Partner(s) of Child Bearing Potential

- Male participants with female partners of childbearing potential are eligible to participate if they agree to the following during the treatment and until the end of relevant systemic exposure.
- Inform any and all partner(s) of their participation in a clinical drug study and the need to comply with contraception instructions as directed by the investigator.
- **Male** participants are required to use a condom for study duration and until the end of relevant systemic exposure defined as **220 days** after the end of treatment.
- Female partners of males participating in the study to consider use of effective methods of contraception until the end of relevant systemic exposure, defined as **160 days** after the end of treatment of the male participant.

- Male participants with a pregnant or breastfeeding partner must agree to remain abstinent from penile vaginal intercourse or use a male condom during each episode of penile penetration during the treatment and until **220 days** after the end of treatment.
- Refrain from donating sperm for the duration of the study treatment and for **220 days**.

Collection of Pregnancy Information

Guidance for collection of Pregnancy Information and outcome of pregnancy on the Pregnancy Surveillance Form.

Pregnancy

If, following initiation of the investigational product, it is subsequently discovered that a study participant is pregnant or may have been pregnant at the time of investigational product exposure, including during at least 5 months after product administration, the investigational product will be permanently discontinued in an appropriate manner (eg, dose tapering if necessary for participant).

The investigator must immediately notify [contact] of this event via either the CIOMS, MedWatch or appropriate Pregnancy Surveillance Form in accordance with SAE reporting procedures.

Protocol-required procedures for study discontinuation and follow-up must be performed on the participant.

Follow-up information regarding the course of the pregnancy, including perinatal and neonatal outcome and, where applicable, offspring information must be reported on the CIOMS, MedWatch, BMS Pregnancy Surveillance Form, or approved site SAE form. A BMS Pregnancy Surveillance Form may be provided upon request.

Any pregnancy that occurs in a female partner of a male study participant must be reported to BMS. Information on this pregnancy will be collected on the Pregnancy Surveillance Form. In order for Sponsor or designee to collect any pregnancy surveillance information from the female partner, the female partner must sign an informed consent form for disclosure of this information.

Overdose

An overdose is defined as the accidental or intentional administration of any dose of a product that is considered both excessive and medically important. All occurrences of overdose must be reported as an SAE.

Other Safety Considerations

Any significant worsening noted during interim or final physical examinations, electrocardiograms, X-rays, and any other potential safety assessments, whether or not these procedures are required by the protocol, should also be recorded as a non-serious or serious AE, as appropriate, and reported accordingly.

9.1. Serious Adverse Event Reporting (SAE) (Appendix B)

It is the responsibility of the PI and the research teams to ensure serious adverse events are reported according to the Code of Federal Regulations, Good Clinical Practices, the protocol guidelines, the sponsor's guidelines, and Institutional Review Board policy.

A serious adverse event (SAE) is any untoward medical occurrence that at any dose, may result in any of the following outcomes:

- Death

- A life-threatening adverse drug experience – any adverse experience that places the patient, in the view of the initial reporter, at immediate risk of death from the adverse experience as it occurred. It does not include an adverse experience that, had it occurred in a more severe form, might have caused death.
- Inpatient hospitalization or prolongation of existing hospitalization
- A persistent or significant disability/incapacity – a substantial disruption of a person's ability to conduct normal life functions.
- A congenital anomaly/birth defect.
- is an important medical event (defined as a medical event(s) that may not be immediately life-threatening or result in death or hospitalization but, based upon appropriate medical and scientific judgment, may jeopardize the subject or may require intervention [eg, medical, surgical] to prevent one of the other serious outcomes listed in the definition above.) Examples of such events include, but are not limited to, intensive treatment in an emergency room or at home for allergic bronchospasm; blood dyscrasias or convulsions that do not result in hospitalization or the development of drug dependency or drug abuse (21 CFR 312.32).
- Suspected transmission of an infectious agent (eg, pathogenic or nonpathogenic) via the study drug is an SAE.
- Any component of a study endpoint that is considered related to study therapy should be reported as an SAE (eg, death is an endpoint, if death occurred due to anaphylaxis, anaphylaxis must be reported).
- An important medical event is defined as a medical event(s) that may not be immediately life-threatening or result in death or hospitalization but, based upon appropriate medical and scientific judgment, may jeopardize the subject or may require intervention [eg, medical, surgical] to prevent one of the other serious outcomes listed in the definition above.) Examples of such events include, but are not limited to, intensive treatment in an emergency room or at home for allergic bronchospasm; blood dyscrasias or convulsions that do not result in hospitalization.)

Important medical events as defined may also be considered serious adverse events. Any important medical event can and should be reported as an SAE.

The following hospitalizations are not considered SAEs in BMS clinical studies:

- a visit to the emergency room or other hospital department < 24 hours, that does not result in admission (unless considered an important medical or life-threatening event)
- elective surgery, planned prior to signing consent
- admissions as per protocol for a planned medical/surgical procedure
- routine health assessment requiring admission for baseline/trending of health status (eg, routine colonoscopy).
- Medical/surgical admission other than to remedy ill health and planned prior to entry into the study. Appropriate documentation is required in these cases.
- Admission encountered for another life circumstance that carries no bearing on health status and requires no medical/surgical intervention (eg, lack of housing, economic inadequacy, caregiver respite, family circumstances, administrative reason).

- Admission for administration of anticancer therapy in the absence of any other SAEs (applies to oncology protocols).

NOTE: Immune-mediated adverse reactions are expected and well described in the package insert for ipilimumab. Hospitalizations required for intravenous administration of high dose steroids will be considered adverse events and will not be considered SAEs. If the adverse event has not improved within 7 days of intravenous high dose steroids, it will be deemed serious and reported in an expedited manner to the appropriate groups.

Important medical events as defined above, may also be considered serious adverse events. Any important medical event can and should be reported as an SAE if deemed appropriate by the Principal Investigators.

All events occurring during the conduct of a protocol and meeting the definition of a SAE must be reported to the IRB in accordance with the timeframes and procedures outlined in “University of Texas M. D. Anderson Cancer Center Institutional Review Board Policy on Reporting Serious Adverse Events”. Unless stated otherwise in the protocol, all SAEs, expected or unexpected, must be reported to IND Office, regardless of attribution (within 5 working days of knowledge of the event).

Serious adverse events will be captured from the time the patient signs consent until **100 days** after the last dose of drug, whether related or not related to the study drug or any protocol related procedure. Serious adverse events must be followed until clinical recovery is complete and laboratory test have returned to baseline, progression of the event has stabilized, or there has been acceptable resolution of the event.

Additionally, any serious adverse events that occur after the 100 day time period that are related to the study treatment must be reported to the IRB as per MDACC policy. This may include the development of a secondary malignancy.

All life-threatening or fatal events, that are unexpected, and related to the study drug, must have written report submitted within 24 hours (next working day) of knowledge of the event to the Safety Project Manager in the IND Office.

Unless otherwise noted, the electronic SAE application (eSAE) will be utilized for safety reporting to the IND Office and MDACC IRB.

Reporting to the FDA:

- Serious adverse events will be forwarded to the FDA by the IND Sponsor (Safety Project Manager IND Office) according to 21 CFR 312.32.

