Preliminary safety data on ipilimumab and SBRT: Combining ipilimumab and SBRT was safe with signs of efficacy (1, 25). In this phase I trial, treatments combining liver or lung SBRT at 50 Gy in 4 fractions or 60 Gy in 10 fractions concurrently or sequentially with ipilimumab at 3 mg/kg for 4 doses were considered safe. Two patients (6%) had DLTs, and even though rates of grade 3 treatment-related toxicity were 34% of treated patients, most were self-limiting and managed as an outpatient. Data on efficacy is encouraging, with 10% out-of-field irPR and 23% clinical benefit. Though these data are encouraging, the outcome may be improved by adding another I-O agent to the treatment regimen: we propose to test the safety and efficacy of combining BMS-986156 with ipilimumab + SBRT. However, there are no clinical data available on the safety of BMS-986156 + Ipilimumab. Treatment group 1 will be initiated to determine the safety of combining BMS-986156 (30 or 100 mg) and ipilimumab (3 mg/kg). After BMS-986156 dose determination in group 1, group 2 will be initiated with BMS-986156 (dose as determined in group 1) and ipilimumab plus SBRT. Recently, in our preclinical model of PD-1 resistance we have shown a dramatic improvement in radiation-induced abscopal responses with the addition of anti-GITR antibody. Moreover, an ongoing study (CA009-002) has recently provided human safety data following administration of a flat dose of nivolumab, another checkpoint inhibitor, in combination with BMS-986156, an anti-GITR monoclonal antibody (26). Altogether, these studies suggest that anti-GITR, a T-cell agonist, may potentiate a T cell mediated response and may contribute to abscopal responses observed when SBRT is administered with checkpoint inhibitors such as ipilimumab or nivolumab. These findings likewise prompted us to include additional arms involving concurrent SBRT administration with anti-GITR plus either ipilimumab or nivolumab in this study. Treatment group 3 will be initiated with nivolumab (480mg) plus BMS-986156 (30mg) and SBRT combination therapy.

Our hypotheses are as follows:

1) SBRT targeting a limited number of liver or lung metastasis in conjunction with ipilimumab and BMS-986156 or nivolumab and BMS-986156 combination therapy will result in improved local and systemic disease control.

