9.2. Reporting of Adverse Events

The investigator (or physician designee) is responsible for verifying and providing source documentation for all adverse events and assigning the attribution for all adverse events for subjects enrolled.

Adverse Events that are routinely collected according to GCP shall be submitted to BMS every three (3) months by the last working day of the third month.

The Adverse Event information required to be sent to BMS is noted in an attached ‘Bristol-Myers Squibb Early Asset Investigator Sponsored Research (ISR) Import Plan’ which describes the method of collection and submission to BMS via the mailbox:

[contact]

When the file is submitted to BMS, it must be noted whether the file contains all Non Serious Adverse Events (only adverse events not previously submitted to BMS within the 3 months).

All Serious Adverse Events must be reported to BMS Worldwide Safety

It is the responsibility of the PI and the research teams to ensure serious adverse events are reported according to the Code of Federal Regulations, Good Clinical Practices, the protocol guidelines, the sponsor's guidelines, and Institutional Review Board policy.

- All Serious Adverse Events (SAEs) that occur following the subject's written consent to participate in the study through 100 days of discontinuation of dosing must be reported to BMS Worldwide Safety, whether related or not related to study drug. If applicable, SAEs must be collected that relate to any later protocol-specified procedure (eg, a follow-up skin biopsy).
- Following the subject's written consent to participate in the study, all SAEs, whether related or not related to study drug, are collected, including those thought to be associated with protocol-specified procedures. The investigator should report any SAE occurring after these aforementioned time periods, which is believed to be related to study drug or protocol-specified procedure.
- An SAE report should be completed for any event where doubt exists regarding its seriousness;
- If the investigator believes that an SAE is not related to study drug, but is potentially related to the conditions of the study (such as withdrawal of previous therapy or a complication of a study procedure), the relationship should be specified in the narrative section of the SAE Report Form.

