 - Other important findings which may be reported by BMS as an Expedited Safety Report (ESR) include: increased frequency of a clinically significant expected SAE, an SAE considered associated with study procedures that could modify the conduct of the study, lack of efficacy that poses significant hazard to study subjects, clinically significant safety finding from a nonclinical (eg, animal) study, important safety recommendations from a study data monitoring committee, or sponsor or BMS decision to end or temporarily halt a clinical study for safety reasons.

Upon receiving an ESR from BMS, the investigator must review and retain the ESR with the IB. Where required by local regulations or when there is a central IRB/IEC for the study, the sponsor will submit the ESR to the appropriate IRB/IEC. The investigator and IRB/IEC will determine if the informed consent requires revision. The investigator should also comply with the IRB/IEC procedures for reporting any other safety information.

SAEs, whether related or not related to study drug, and pregnancies must be reported to BMS within 24 hours \ 1 Business Day of becoming aware of the event. SAEs must be recorded on either CIOMS, MedWatch, or approved site SAE form.

Pregnancies must be reported and submitted to BMS. BMS will perform due diligence follow-up using the BMS Pregnancy Form which the investigator must complete.

SAE Email Address: [contact]

SAE [contact]

If only limited information is initially available, follow-up reports are required. (Note: Follow-up SAE reports should include the same investigator term(s) initially reported.)

If an ongoing SAE changes in its intensity or relationship to study drug or if new information becomes available, a follow-up SAE report should be sent within 24 hours \ 1 Business Day to BMS using the same procedure used for transmitting the initial SAE report.

All SAEs should be followed to resolution or stabilization.

The causal relationship to study drug is determined by a physician and should be used to assess all adverse events (AE). The causal relationship can be one of the following:

- Related: There is a reasonable causal relationship between study drug administration and the AE.
- Not related: There is not a reasonable causal relationship between study drug administration and the AE.

The term "reasonable causal relationship" means there is evidence to suggest a causal relationship.

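### The section 9.1 note on admissions for IV high-dose steroids contradicts the protocol's own hospitalization criterion for an SAE, and removes or delays SAE reporting for those admissions

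*Combined protocol and SAP*

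**What the plan says.** Section 9.1 lists the outcomes that make an event serious. One is "Inpatient hospitalization or prolongation of existing hospitalization", with no exception for the treatment given. The section then lists admissions that do not count: short emergency visits without admission, planned or protocol-driven procedures, routine assessments, social or administrative stays, and admissions to give anticancer therapy.

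A separate note follows that list. It opens with its reason: "Immune-mediated adverse reactions are expected and well described in the package insert for ipilimumab". Its rule is "Hospitalizations required for intravenous administration of high dose steroids will be considered adverse events and will not be considered SAEs". It then sets a limit: "If the adverse event has not improved within 7 days of intravenous high dose steroids, it will be deemed serious", with expedited reporting from that point.

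Three other statements bear on this:

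- Section 3.3: "there are no clinical data available on the safety of BMS-986156 + Ipilimumab".
- Section 9.1, on reporting to the IND Office: "Unless stated otherwise in the protocol, all SAEs, expected or unexpected, must be reported to IND Office, regardless of attribution".
- Section 9.2, on reporting to the drug supplier: "SAEs, whether related or not related to study drug, and pregnancies must be reported to BMS within 24 hours" (or one business day). Adverse events that are not SAEs go to the supplier in a file every three months.

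**The concern.** The note settles seriousness by how the event is treated and whether it was expected. Seriousness in section 9.1 depends on outcome, and the section itself treats expectedness as a separate matter, since it asks for expected as well as unexpected SAEs.

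The expectedness argument also has a narrow base. It rests on the ipilimumab label, while groups 1 and 2 receive ipilimumab with an agent for which the protocol reports no combined clinical safety data. Group 3 receives nivolumab with BMS-986156 and SBRT. The sentence that creates the exemption names neither ipilimumab nor immune-mediated events. Read literally, it could cover an admission for radiation pneumonitis treated with IV steroids; read with the sentence before it, it covers immune-mediated reactions only. The text does not say which.

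At stake is prompt notice of severe toxicity in a trial whose primary objectives are safety, with 10 patients planned per dose level in group 1. Sites could also classify the same admission differently, depending on which part of section 9.1 they apply.

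**Working it through.** The plan gives no figure to reproduce here. The check compares the rules and then sets a scale.

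**1. The two rules side by side.** Take an unplanned admission of more than 24 hours for IV high-dose steroids to treat a drug toxicity that improves by day 5.

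- Section 9.1 criteria list: inpatient hospitalization, so an SAE.
- Section 9.1 note: an adverse event, not an SAE.

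The listed exclusions do not resolve this. They concern stays that are planned, administrative, not true admissions, or for giving anticancer therapy. Only the note exempts an unplanned admission to treat toxicity.

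**2. What changes in reporting to the supplier (section 9.2).**

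| Event | Under the criteria list | Under the note |
|---|---|---|
| Improves within 7 days, no other criterion met | 24 hours / 1 business day | three-monthly file |
| Not improved within 7 days, no other criterion met | 24 hours / 1 business day | deemed serious after 7 days of steroids, then expedited: about 7 days late |
| Meets another criterion (death, life-threatening, disability) or potential drug-induced liver injury | 24 hours / 1 business day | unchanged |

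**3. Whether DLT assessment covers the gap.** Section 5.1.9 gives a median onset of grade 3–5 immune-related events of 7 to 9 weeks with ipilimumab, that is 7 × 7 = 49 to 9 × 7 = 63 days. Section 7.2 sets the DLT window at 29 days for group 1 and 43 days for group 2. The earliest median is 49 − 29 = 20 days after the group 1 window and 49 − 43 = 6 days after the group 2 window. If onset in this trial resembles those studies, at least half of such events would start after DLT assessment has closed. The first cohort safety summaries in section 10 are due at the same 29 and 43 days.

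**4. Scale.** Inputs:

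- Ipilimumab patients: 20 (group 1) + 20 (group 2) = 40 (section 10.1).
- Grade 3/4 immune-related event rate at 3 mg/kg ipilimumab alone: 6.3–13% (section 5.1.8). Applying it here is an assumption.

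Expected patients with such an event: 40 × 0.063 = 2.5 to 40 × 0.13 = 5.2.

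Chance of at least one, with independent patients: 1 − (1 − 0.063)^40 = 0.926 to 1 − (1 − 0.13)^40 = 0.996.

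Let s be the share admitted for IV high-dose steroids with no other seriousness criterion met. The number losing SAE status or reported late is 40 × rate × s. The documents do not give s. With s between 0 and 1, the result runs from 0 to about 5.

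**The case against.** The strongest reply is that the safety data remain intact, and much of it stands. Non-serious events are collected throughout treatment and for at least 100 days afterwards (section 9). They are graded, count as DLTs within the window if they meet the criteria, enter the grade 3 or higher comparison (section 10.2.3), and can appear in the cohort summaries sent to the IND Office after every 3 evaluable patients per group. The planned analysis is by grade, not by SAE status. A reader might infer that the note conceals these events; the documents do not support that. What is lost is SAE status and prompt reporting.

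The exemption also has limits. Other seriousness criteria still apply at once, so a general 7-day delay cannot be claimed. Potential drug-induced liver injury is always an SAE. Grade 3/4 ipilimumab hypersensitivity is documented as an SAE (section 7.6.1), and grade 3/4 infusion reactions with the other agents go to the supplier's monitor within 24 hours (section 7.4.2). Important medical events may still be reported as SAEs, though the sentence after the note leaves that to the principal investigators.

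A conflict with section 9.2 is tempting to assert, given "An SAE report should be completed for any event where doubt exists regarding its seriousness". But section 9.2 governs how SAEs are reported, while the note says what counts as one and so arguably removes the doubt. The IND Office duty carries a proviso for anything the protocol states otherwise. The firm contradiction lies within section 9.1. An effect on FDA reporting cannot be shown either: section 9.1 only refers to a regulation that the documents do not reproduce.

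Finally, a reader might size the problem from the 34% grade 3 treatment-related toxicity in the prior ipilimumab and SBRT trial (section 3.3). If a quarter to a half of those events needed admission for steroids, 60 × 0.34 × 0.25 = 5.1 to 60 × 0.34 × 0.50 = 10.2 admissions would result. That does not hold. The same sentence says most of these toxicities resolved by themselves and were handled without admission. The 34% is not specific to immune-mediated events, and it would be applied to a group without SBRT and a group without ipilimumab.

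**Conclusion.** The point holds as an internal contradiction with a limited but real effect on reporting. The note overrides the hospitalization criterion on the ground of expectedness, using one drug's label in a trial that goes beyond that drug. Admissions that improve on steroids and meet no other criterion move from a 24-hour report to a three-monthly file; the rest are reported about 7 days late. Routine collection and grading remain, but they do not give prompt notice, and DLT assessment is only a partial backstop because typical onset falls after its window.

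The scale of 0 to about 5 affected events is an expected count. It rests on the ipilimumab-alone rate and an unknown admission share, and is not a ceiling: the rate with BMS-986156 is unknown and could be higher, and group 3 is not counted. It should not be read as applying to an untested drug pair in every group. The lack of clinical safety data concerns ipilimumab with BMS-986156 in groups 1 and 2; the group 3 pair had been given to 225 subjects, though not with SBRT (section 7.1.1.3).

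**What to change.** Reconcile the note with the criteria list in section 9.1. Either delete it, or limit it so that any admission meeting the hospitalization criterion is recorded and reported as an SAE from the time of awareness, whatever treatment is given. Record expectedness as a separate item on the SAE form, so that a known ipilimumab reaction can still be identified as such. If any form of the note is kept, it should say which drugs and which types of event it covers.

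The change is to protocol wording only and alters no treatment. It costs some additional SAE forms: on the assumption used above, about 5 at most in expectation across groups 1 and 2, plus any from group 3.
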